2.2.2 Randomization and Blinding

2.2.2.1 Randomization

Patients who meet all inclusion criteria and no exclusion criteria will be randomized to one of three dose levels of Ziltivekimab (7.5 mg, 15 mg or 30 mg) or placebo for a 24 Week Treatment Period. Treatments will be assigned to randomized patients via an Interactive Web-Response System (IWRS). 240 patients will be randomized in a 1:1:1:1 ratio (60 per group) to Ziltivekimab 7.5 mg, Ziltivekimab 15 mg, Ziltivekimab 30 mg, or matching Placebo. Patients will be stratified

by baseline hemoglobin (≥ 11 or < 11 g/dL) and CKD stage (3, 4 or 5). Note that CKD stage is stratified into two categories: (1) stage 3 and (2) stages 4 and 5.

2.2.2.2 Blinding

This study is double-blind. The patients, investigators, site personnel, site monitors and Sponsor and the Contract Research Organization (CRO) clinical operational personnel will be blinded to the treatment assignment. Ziltivekimab and matching placebo will be provided as a liquid for subcutaneous injection.

The randomization list will be generated by a CRO statistician not otherwise involved in the study.

2.2.2.3 Unblinding

In case of a medical emergency or medical situation in which the treatment assignment is necessary for proper patient management, the Investigator may obtain the treatment assignment from the IWRS. The Investigator should make every reasonable attempt to contact the Medical Monitor before unblinding a patient. In all cases, the Investigator must submit a written report, including all pertinent details, to the Medical Monitor within 24 hours of the unblinding.

2.2.3 Study Drug

The study drug regimens and the matching placebo regimen to be examined in this study are:

- Dose #1: Ziltivekimab, 7.5 mg per injection, administered 6 times (every 28-days) on Weeks 1, 5, 9, 13, 17, and 21 as a subcutaneous injection.
- Dose #2: Ziltivekimab, 15 mg per injection, administered 6 times (every 28-days) on Weeks 1, 5, 9, 13, 17, and 21 as a subcutaneous injection.
- Dose #3: Ziltivekimab, 30 mg per injection, administered 6 times (every 28-days) on Weeks 1, 5, 9, 13, 17, and 21 as a subcutaneous injection.
- Matched placebo injections administered subcutaneously 6 times (every 28 days) at the same frequency as the active treatment on Weeks 1, 5, 9, 13, 17, and 21.

Patients should receive 6 injections of their assigned dose during the trial. The total cumulative dosage will be 45 mg for those patients randomized to 7.5 mg per injection, 90 mg for those patients randomized to 15 mg per injection, and 180 mg for those patients randomized to 30 mg per injection.

2.2.4 Sample Size Determination

Approximately 240 patients (60 per group) will be randomized.

The primary efficacy endpoint is percent change from baseline in hs-CRP (average of the hs-CRP value prior to randomization and Day 1) to Week 13 between each active group and placebo. Based on the observed treatment difference in percent change from baseline in hs-CRP of -60.74% between combined COR-001-01 active groups and placebo and the associated pooled SD of 16.893% in hs-CRP at Week 4 from the final analysis of study COR-001-SC1, a sample size of 54 per group yields more than 99% power with 2-sided alpha=0.05. Taking into consideration the dropout rate of 10% by the end of the study, a sample size of 60 per group is planned for this study.

2.3 Study Endpoints

2.3.1 Primary Endpoint

The primary endpoint of this study is the difference in percent change in hs-CRP levels from Baseline (average of the hs-CRP value prior to randomization and Day 1) to Week 13 between each active group and placebo.

2.3.2 Secondary Endpoints

The secondary endpoints are as follows:

- Difference in change in SAA from Baseline to Week 13 between each active group and placebo.
- Difference in percent change in fibrinogen from Baseline to Week 13 between each active group and placebo.

2.3.3 Exploratory Efficacy Endpoints

The exploratory efficacy endpoints are listed below:

- Difference in percent change in hs-CRP levels from baseline to End of Treatment (weeks 23 through 24) between each active group and placebo.
- Difference in percent change in serum NT-pro-BNP from Baseline (average of NT-pro-BNP value prior to randomization and Day 1) to Week 13 and to End of Treatment (Weeks 23 through 24) between each active group and placebo.
- Difference in change in SAA from Baseline to End of Treatment (Weeks 23 through 24) between each active group and placebo.
- Difference in percent change in fibrinogen from Baseline to End of Treatment (Week 24) between each active group and placebo.
- Difference in change in hemoglobin from Baseline (average of the two most recent hemoglobin values prior to randomization and Day 1) to Week 13 and to End of Treatment (Weeks 23 through 24) between each active group and placebo.
- Difference in change in serum albumin from Baseline (average of the two most recent serum albumin values prior to randomization and Day 1) to Week 13 and to End of Treatment (Weeks 23 through 24) between each active group and placebo.
- Proportion of patients achieving hs-CRP response at Week 13 and to End of Treatment (Weeks 23 through 24), defined as hs-CRP <2.0 mg/L in each active group and placebo.
- Difference in change in ST2 from Baseline to Week 13 to End of Treatment (Week 24) between each active group and placebo.
- Difference in percent change in Lp (a) from Baseline to Week 13 and to End of Treatment (Weeks 23 through 24) between each active group and placebo.
- Difference in percent change in LDL-C, triglycerides, ApoB, ApoA1, ApoB/ApoA1, and lipid profile by NMR spectroscopy from Baseline to Week 13 and to the End of Treatment (Weeks 23 through 24) between each active group and placebo.

- Difference in change of creatinine based eGFR and cystatin C-based eGFR from Baseline to Week 13 and to the End of Treatment (Weeks 23 through 24) between active group and placebo.
- Difference in change of UACR from Baseline to Week 13 and to the End of Treatment (Weeks 23 through 24) between active group and placebo.
- Difference in change of the total fatigue score (PROMIS Fatigue 13a short form and selected items from the PROMIS fatigue item bank) from Baseline to Week 13 and to End of Treatment (Weeks 23 through 24) between each active group and placebo.
- Difference in change of the PROMIS interest in sexual activity item from Baseline to Week 13 and to End of Treatment (Week 24) between each active group and placebo.
- Difference in change of the Corvidia ePRO items from Baseline to Week 12 and to End of Treatment (Weeks 23 through 24) between each active group and placebo.
- Difference in change of the PGIS index from Baseline to Week 12 and to End of Treatment (Week 24) between each active group and placebo.
- Descriptive analyses of the PGIC index at Weeks 5, 13, and End of Treatment (Week 24) in each active group and placebo.
- Difference in change of the Optum SF-36 v2® Health Survey physical component summary (PCS), mental component summary (MCS) and domain scores from Baseline to Week 13 and to End of Treatment (Weeks 23 through 24) between each active group and placebo.
- Difference in change of the EQ-5D-5L index from Baseline to Week 12 and to End of Treatment (Week 24) between each active group and placebo.
- Evaluation of the psychometric properties of the PROMIS Fatigue 13a short form and selected items from the PROMIS Fatigue item bank and the Corvidia ePRO items in CKD patients – to be described in a PRO psychometric analysis plan (PAP).
- Descriptive analyses by dose and treatment may be conducted on samples stored for analysis of exploratory biomarkers, genomic and transcriptomic analysis.
- Difference in change in TSAT from Baseline to peak level, Week 13, and the End of Treatment (Weeks 23 through 24), between each active group and placebo.
- Difference in change in CHr from Baseline to peak level, Week 13, and to End of Treatment (Week 24) between each active group and placebo.
- Difference in change in TIBC from Baseline to Week 13 and to End of Treatment (Weeks 23 through 24) between each active group and placebo.
- Difference in change in serum ferritin from Baseline to Week 13 and to End of Treatment (Weeks 23 through 24) between each active group and placebo.
- Difference in change in serum iron from Baseline to Week 13 and to End of Treatment (Weeks 23 through 24) between each active group and placebo.

- Difference in change in serum hepcidin from Baseline to Weeks 13 and to End of Treatment (Week 24) between each active group and placebo.
- Difference in percent change in serum NT-pro-BNP from Baseline to Week 13 and to End of Treatment (Weeks 23 through 24) between each active group and placebo in patients with baseline NT-pro-BNP > 250 pg/mL.
- Difference in change in hemoglobin from Baseline (average of the two most recent hemoglobin values prior to randomization and Day 1) to Week 13 and to End of Treatment (Weeks 23 through 24) between each active group and placebo in patients with baseline hemoglobin < 11 g/dL.
- Difference in change in serum albumin from Baseline (average of the two most recent serum albumin values prior to randomization and Day 1) to Week 13 and to End of Treatment (Weeks 23 through 24) between each active group and placebo in patients with baseline albumin < 4.0 g/dL.

2.3.4 Calculation/Derivation of Endpoint Variables

2.3.4.1 PROMIS Fatigue 13a Short Form

The PROMIS Fatigue 13a short form contains 13 items that assess symptoms and impacts of fatigue. The PROMIS Fatigue 13a short form will be scored using item-level analysis according to the scoring manual. The PROMIS fatigue 13a short form and selected PROMIS items can be found in Appendix B of the protocol. The scoring manual for PROMIS Fatigue can be found at: http://www.healthmeasures.net/images/PROMIS/manuals/PROMIS_Fatigue_Scoring_Manual.pdf.

Each question from the PROMIS Fatigue 13a short form has five response options (1= Not at all, 2=A little bit, 3=Somewhat, 4=Quite a bit, 5=Very much). To use the scoring tables from the PROMIS fatigue scoring manual, a summed score is calculated. The lowest possible summed score is 13 and the highest possible summed score is 65. All questions must be answered in order to produce a valid score using the scoring tables. Once calculated, the total summed raw score is translated to a T-score. The T-score rescales the raw score into a standardized score with a mean of 50 and a standard deviation (SD) of 10. The T-score and standard error are then used to calculate the 95% confidence interval around the observed score. The 95% confidence interval is calculated as T-Score $\pm 1.96 \times \text{SE}$. The T-score will not be calculated if a response is missing for one or more question from the PROMIS Fatigue 13a short form.

A higher PROMIS T-score represents more fatigue.

2.3.4.2 PROMIS Sexual Function and Satisfaction (PROMIS SexFS)

The PROMIS SexFS is a customizable self-reported set of measures that includes 79 items in 11 domains. For the purpose of this protocol, only one item will be used: interest in sexual activity. This item has five response options (1= Not at all, 2=A little bit, 3=Somewhat, 4=Quite a bit, 5=Very much). The PROMIS evaluations will be done on a subject's device at the clinic PRIOR to dosing.

2.3.4.3 Optum SF-36 v2® Health Survey

The Optum SF-36 v2® Health Survey is perhaps the most widely used health-related quality of life (HRQoL) survey instrument in the world today. It is comprised of 36 items that assess eight health concepts: physical functioning, role limitations caused by physical health problems, role

limitations caused by emotional problems, social functioning, emotional well-being, energy/fatigue, pain, and general health perceptions (see Appendix C of the protocol). Physical and mental health summary scores are also derived from the eight Optum SD-36 scales. The Optum evaluations will be done on a subject's device at the clinic PRIOR to dosing. Optum's PRO CoRE software version 1.5 will be used to score SF-36 data.

2.3.4.4 CARES Corvidia ePRO

The CARES Corvidia ePRO is a new PRO instrument under development (see Appendix D of the protocol). It consists of 19 symptom items, with a 24-hour recall, asking patients to report their worst level of that symptom in the past 24 hours on a numeric rating scale from 0 (no symptom) to 10 (symptom as bad as I can imagine).

Data will be collected at home on subject's personal device or one provided by Corvidia; the questionnaire will be answered daily for 7 days prior to dose (Screening prior to Dose 1 (Visit 1), Dose 2 (Visit 4), Dose 4 (Visit 7), and the last 2 weeks after Dose 6 (Visit 23-24). For each item, weekly scores will be derived as the average of the 7 consecutive daily scores as follows

Baseline = average of Day -7 to Day -1

Visit 4 = average of Day 22 to Day 28

Visit 7 = average of Day 78 to Day 84.

If more than 4 daily scores out of the 7 days (>50%) within the weekly period are missing, then the score is set to missing.

A bi-weekly score (the End of Treatment) will also be derived as the average of Day 155 to Day 168. If more than 8 daily scores out of the 14 days (>50%) within the bi-weekly period are missing, then the score is set to missing.

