4.2. PRO VARIABLES

4.2.1. CARES CORVIDIA ePRO

For each item, weekly scores will be derived as the average of the 7 consecutive daily scores as follows:

- Baseline = average of Day -7 to Day -1
- Week 5 (Visit 4) = average of Day 22 to Day 28
- Week 13 (Visit 7) = average of Day 78 to Day 84
- Week 24 (Visit 11) = average of Day 155 to Day 168

For Baseline, Week 5 and Week 13, if more than 3 daily scores out of the 7 days (>50%) within the weekly period are missing, then the score is set to missing.

For Week 24, if more than 7 daily scores out of the 14 days (>50%) within the bi-weekly period are missing, then the score is set to missing.

Document: \\ieedc-vnasc01\Sites\ [REDACTED]\NLHOF\IntProjects\Consulting\Projects\ Corvidia\ [REDACTED]\Biostatistics\01.Documentation\02.SAPI Corvidia_RESCUE_PROSAP_v2.0_21JUL2020
Author: [REDACTED] Version No: v.2.0
Template No.: [REDACTED] Version Date: 21JUL2020
Effective Date: 01Dec2018 Reference: [REDACTED]

Preliminary scoring of the CARES includes the calculation of a Total Symptom Score (TSS). Alternative means of scoring the CARES will be explored in a separate psychometric analysis plan (PAP) and if any derived, these will be included in this SAP for efficacy analysis. Additional scales and subscales may be derived based on the results of the psychometric analysis plan (PAP). A higher score for the TSS or other scales/subscales represent more symptoms.

Change from baseline defined as post-baseline value minus baseline value will be calculated for each assessment. At each post-baseline assessment, the change in score from baseline will be calculated for each scale/item.

Domain scores may result from the psychometric analyses described in a separate PAP. In this PAP, clinically meaningful thresholds for these potential domains will also be derived. Change from baseline in the TSS score, as well as the domain scores that may result from the psychometric analysis, will be categorized at each visit as improvement/stable/deterioration using the clinically meaningful threshold value for change scores derived in the psychometric analyses as follows:

- Improvement: a change from baseline \leq -threshold points;
- Deterioration: a change from baseline \geq threshold points
- No change: a change from baseline between (-threshold to threshold).

Sensitivity analyses may be performed if more than one threshold values are suggested by the psychometric analyses.

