2.3 End of Treatment: CARES Corvidia ePRO and other PRO outcomes

According to section 2.3.4.4 of the SAP version 1.0, a bi-weekly score (the End of Treatment) for the CARES Corvidia ePRO will be derived as the average of Day 155 to Day 168. If ≥ 8 daily scores out of the 14 days ($>50\%$) within the bi-weekly period are missing, then the score is set to missing.

However, for patients who discontinued due to COVID19 after Week 13 and did not complete the end of treatment visit or did not enter their data on their personal device, the end of treatment will be assigned using the average of values from Visit 7 (Day 78 to Day 84). If ≥ 4 daily scores out of the 7 days ($>50\%$) within the weekly period are missing, then the score is set to missing.

For PRO outcomes PROMIS Fatigue 13a Short Form and Optum SF-36 v2®Health Survey where assessments are entered at Visit 1 (Baseline), Visit 4 (Week 5), Visit 7 (Week 13), Visit 10 (Week 23), and Visit 11 (Week 24), the end of treatment visit will be defined as the average of assessments at Week 23 and Week 24.

For PRO outcomes PROMIS Sexual Function and Satisfaction, EurQol-5D-5L, and Patient Global Impression of Change where assessments are entered at Visit 1, Visit 4 (Week 5), Visit 7 (Week 13), and Visit 11 (Week 24), the end of treatment visit will be defined as the assessment at Week 24.

For PRO outcome Patient Global Impression of Severity where assessments are entered at the end of Week -1, end of Week 4, end of Week 12, and at Week 24, the end of treatment visit will be defined as the assessment at Week 24.

For all PRO outcomes described above, for patients who discontinued due to COVID19 after Week 13, the end of treatment visit will be defined as the last assessment after Week 13. If there are no visits after Week 13, then Week 13 will be considered the End of Treatment visit.

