6.1.1. VARIABLES GENERATED FROM CARES

For each item, weekly scores will be derived as the average of the 7 consecutive daily scores as follows:

Baseline = average of Day -7 to Day -1

Week 5 (Visit 4) = average of Day 22 to Day 28

Week 13 (Visit 7) = average of Day 78 to Day 84

Week 24 (Visit 11) = average of Day 155 to Day 168

For Baseline, Week 5 and Week 13, if more than 3 daily scores out of the 7 days (>50%) within the weekly period are missing, then the score is set to missing.

For Week 24, if more than 7 daily scores out of the 14 days (>50%) within the bi-weekly period

Document : /Users/[REDACTED]/Dropbox (Corvidia Tx)/Corvidia Tx Team Folder/Assets/COR-001/Clinical/RESCUE (COR-001-02)/Manuals & Plans/PRO PAP/Corvidia_RESCUE_PAP_FinalV2.0_24APR2020.docx

Author: [REDACTED] Version No: V2.0

Version Date: 24APR2020

Template No.: [REDACTED] Reference: [REDACTED]

Effective Date: 01Dec2018

Copyright © 2018 [REDACTED] All rights reserved. The contents of this document are confidential and proprietary to [REDACTED] and its subsidiaries. Unauthorized use, disclosure or reproduction is strictly prohibited.

are missing, then the score is set to missing.

Preliminary scoring of the CARES includes the calculation of a Total Symptom Score (TSS). Alternative means of scoring the CARES that are derived from the factor analyses and conceptual considerations may also be defined if supported by the data and if the research team considers these to be plausible and clinically useful alternatives. The following conceptual domains from CARES will be considered: physiological (Short Breath, Swelling, Fatigue, Weakness, Light-headedness, Decreased Appetite, Nausea), psychological (Depression, Concentration, Forgetfulness), pain (Bone / Joints, Nerves, Muscle Cramps), and sensorial (Hand numbness/tingling, Uncomfortable legs, Itching, Dry skin, Dry mouth, Cold) symptoms.

In the preliminary scoring, the daily TSS will be calculated as the average of the 19 daily item scores. A daily TSS score will be calculated if at least 10 out of the 19 items (> 50%) are non-missing. The TSS weekly score will be calculated in the same fashion as the individual items. Higher TSS indicate more symptoms/poorer outcomes.

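### The clinical SAP drops a weekly CARES score only from 5 of 7 missing days, one day later than its own >50% label and than the PRO SAP v2.0 and PAP v2.0; the addendum corrects this only in part

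*SAP*

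**What the plan says.** Clinical SAP v1.0, section 2.3.4.4, derives a weekly score for each CARES item at Baseline (Days -7 to -1), Visit 4 (Days 22 to 28) and Visit 7 (Days 78 to 84). The score is set to missing under this condition: "If more than 4 daily scores out of the 7 days (>50%) within the weekly period are missing". For the End of Treatment score over Days 155 to 168 the condition is "If more than 8 daily scores out of the 14 days (>50%) within the bi-weekly period are missing".

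PRO SAP v2.0, section 4.2.1, uses the same items and day ranges but different counts. For Baseline, Week 5 and Week 13 it is "if more than 3 daily scores out of the 7 days (>50%) within the weekly period are missing", and for the 14-day score "For Week 24, if more than 7 daily scores out of the 14 days (>50%) within the bi-weekly period are missing". PAP v2.0, section 6.1.1, has the same two limits as the PRO SAP.

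The addendum to the clinical SAP, section 2.3, gives the 14-day limit as 8 or more missing days and attributes it to section 2.3.4.4. It then lets the Visit 7 week serve as End of Treatment for patients who discontinued due to COVID19 after Week 13 and lack the End of Treatment visit or device data. For that substituted week the condition is "If ≥ 4 daily scores out of the 7 days". The summary of changes in the addendum's introduction lists no change to either limit.

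**The concern.** A count and a percentage in the same sentence should give the same rule. In section 2.3.4.4 they do not, so a programmer must choose between them. The choice decides whether a week with exactly 4 missing days yields a score.

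Two consequences follow. First, the clinical and PRO datasets can disagree about which weekly item scores exist. At Baseline this carries furthest, because a patient without a baseline score has no change from baseline at any visit. Second, the clinical analysis can disagree with itself. Under clinical SAP section 5, the MMRM uses visits up to Week 13 and the End of Treatment comparison uses ANCOVA. After the addendum, one diary week can enter the first as observed and the second as missing.

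**Working it through.** **Inputs.** The limits stated in clinical SAP 2.3.4.4, addendum 2.3, PRO SAP v2.0 4.2.1 and PAP v2.0 6.1.1.

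**Step 1: what the label means as a count.** Find the smallest number of missing days m with m/n > 0.5.

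- n = 7: 3/7 = 42.9% and 4/7 = 57.1%, so m = 4 (more than 3).
- n = 14: 7/14 = 50.0% and 8/14 = 57.1%, so m = 8 (more than 7).

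**Step 2: what each document does.** First number of missing days at which the score is dropped:

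| Document | 7-day score | 14-day score |
|---|---|---|
| Clinical SAP 2.3.4.4 | 5 (71.4%) | 9 (64.3%) |
| Addendum 2.3 | 4 (57.1%), substituted Visit 7 week only | 8 (57.1%) |
| PRO SAP v2.0 4.2.1 | 4 (57.1%) | 8 (57.1%) |
| PAP v2.0 6.1.1 | 4 (57.1%) | 8 (57.1%) |

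The clinical SAP's label cannot be reproduced from its counts. Reading its two limits as at least 4 and at least 8 restores agreement. Reading the label as at least 50% does not, since that gives 4 of 7 and 7 of 14.

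**Step 3: one week, two answers.** Take a patient who discontinued due to COVID19 after Week 13, has no End of Treatment data, and has exactly 4 of the 7 days missing in Days 78 to 84. As the Visit 7 score, 4 is not more than 4, so the score is kept. As the End of Treatment score, 4 meets the addendum's limit, so it is set to missing.

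**Step 4: how often the rules disagree.** They disagree only at exactly 4 of 7 (or exactly 8 of 14) missing days. The documents give no diary missingness rate, so the daily rate p is an assumption, as is independence between days.

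P(exactly 4 of 7) = 35 × p^4 × (1 − p)^3:

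- p = 0.1: 35 × 0.0001 × 0.729 = 0.3%
- p = 0.2: 35 × 0.0016 × 0.512 = 2.9%
- p = 0.3: 35 × 0.0081 × 0.343 = 9.7%
- p = 0.4: 35 × 0.0256 × 0.216 = 19.4%

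P(exactly 8 of 14) = 3003 × p^8 × (1 − p)^6, which gives about 0%, 0.2%, 2.3% and 9.2% at the same rates.

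**The case against.** Several points can fairly be made in the plan's defence.

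- **The 14-day limit is mostly settled.** The addendum is later than clinical SAP v1.0 and gives 8 or more, which agrees with the PRO SAP v2.0 and PAP v2.0. This stands. What remains is that the addendum presents the figure as what 2.3.4.4 already says and does not list it as a change.
- **The two plans mostly test different variables.** A reader might infer that the same CARES endpoint will come out differently in the two reports. The documents do not support that. Clinical SAP sections 2.3.3 and 3.4.3 analyse change in CARES items. PRO SAP sections 5.6 to 5.8 model the total symptom score and any subscales, and 5.6 says that analyses in the clinical SAP are not repeated. The overlap is the weekly item scores and item changes of PRO SAP 4.2.1 and their patient counts. There, values may differ.
- **The Visit 7 conflict is narrow.** It needs a COVID19 discontinuation after Week 13, no End of Treatment data, and exactly 4 missing days in one week. This stands as a limit on size, not as a reconciliation of the two rules.
- **A score from 3 of 7 days is not shown to be poor.** No document says that 3 observed days are too few. The defect is the mismatch with the label and with the companion plans.
- **The intended rule can be guessed.** The label, the PRO SAP, the PAP and the addendum all point to 4 or more. That makes the correction easy, but the 7-day rule for Baseline, Visit 4 and Visit 7 in the clinical SAP still reads otherwise.

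**Conclusion.** The point holds for the 7-day limit. Section 2.3.4.4 is one day out against its own percentage and against PRO SAP v2.0 and PAP v2.0, and the addendum leaves Baseline, Visit 4 and Visit 7 as they were. For the 14-day limit only an undeclared correction remains.

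The effect is confined to weekly item scores with exactly 4 of 7 days missing. The range of 0.3% to 19.4% of weeks rests on assumed daily rates of 10% to 40% and on independence between days; nothing in the documents favours any part of it. If missing days cluster within patients, the share could differ in either direction.

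CARES is an exploratory endpoint. The primary (hs-CRP) and secondary (SAA, fibrinogen) results are unaffected, and nothing here implies bias towards either arm. The matter should be corrected, but it is a scoring inconsistency of modest reach.

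**What to change.** In clinical SAP 2.3.4.4, or in the addendum, state that a CARES score is set to missing when 4 or more of 7 daily scores are missing at Baseline, Visit 4 and Visit 7, and when 8 or more of 14 are missing for End of Treatment. List both in the summary of changes as corrections to 2.3.4.4, and do not attribute the 14-day figure to that section as it now reads.

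The cost is two numbers and one line in the change list. If CARES scores have already been derived with the limits in 2.3.4.4, the derivation must be rerun. A count of patient-weeks with exactly 4 of 7 or 8 of 14 days missing would then replace the assumed rates above.
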